3.2.4 Participant Input into Design

Patient research partners, [name] and [name], are included in the project group. They have provided input on the relevance of the research question, the feasibility of the study design from a patient perspective and written information to patients. They will continue their involvement for the continuation of the study.

3.3 End of Study Definition

A participant is considered to have completed the study if he/she has completed all phases of the study including the last visit. The study period is 18 months, with a possible extension to 36 months, which will be decided by the study project group. The end of the study is defined as the date of the last visit of the last participant in the study.

4 Study Population

4.1 Inclusion Criteria

Participants are eligible to be included in the study only if all the following criteria apply:

- Male or female >18 years of age at screening
- Patients with a diagnosis of axSpA who fulfil the diagnostic ASAS criteria for axSpA (see Appendix 9.4)
- Stable medical treatment with TNFi the last 6 months
- Inactive or low disease activity (ASDAS<2.1) at inclusion
- Capable of understanding the Norwegian language and of signing an informed consent form

4.2 Exclusion Criteria

Participants are excluded from the study if any of the following criteria apply:

Medical conditions:

- Major co-morbidities, such as severe malignancies, severe diabetes mellitus, severe infections, uncontrollable hypertension, severe cardiovascular disease (NYHA class III or IV), severe respiratory diseases, and/or cirrhosis.
- Indications of active tuberculosis (TB)
- Pregnant or nursing

Diagnostic assessments:

- Abnormal renal function, defined as serum creatinine >142 µmol/L in female and >168 µmol/L in male, or glomerular filtration rate (GFR) <40 mL/min/1.73 m²
- Abnormal liver function (defined as Alanine Transaminase (ALT) >3x upper normal limit), active or recent hepatitis
- Leukopenia and/or thrombocytopenia

Other:

- Severe psychiatric or mental disorders, alcohol abuse or other substance abuse, language barriers or other factors which makes adherence to the study protocol impossible

4.3 Lifestyle Considerations

Female patients planning pregnancy within the study period will not be recruited as this will induce a different follow-up pattern not compatible with this study design. No lifestyle changes are otherwise required for participation in the study.

4.4 Screen Failures

Screen failures are defined as participants who consent to participate in the clinical study but are not subsequently randomly assigned to study intervention. A minimal set of screen failure information is required to ensure transparent reporting of screen failure participants to meet the Consolidated Standards of Reporting Trials (CONSORT) publishing requirements and to respond to queries from regulatory authorities. Minimal information includes demography, screen failure details, eligibility criteria, and any serious adverse event (SAE).

Individuals who do not meet the criteria for participation in this study (screen failure) may be rescreened.

[figure not shown]
5 Study Intervention

5.1 Study intervention

The ReMonit study is a randomized, controlled study with three parallel arms, and the design is illustrated in Figure 1. AxSpA patients are randomized 1:1:1 to either:

- a. Usual care: conventional follow-up strategy with pre-scheduled visits at the hospital every 6th month with a review of disease-related concerns, blood test results, joint examination, medication use, and adverse events
 - or
- b. Remote monitoring: hospital health professionals (HPs) perform remote monitoring of frequent PROs and blood test results
 - or
- c. Patient-initiated care: no pre-scheduled visits or remote monitoring

Figure 1: Illustration of the ReMonit study design.

5.1.1 Medical treatment for all three arms

The medical treatment will be the same for all three study arms and will follow the current treatment recommendations for axSpA¹⁵. At inclusion, all patients will have low disease activity. The treatment target for all three study arms is that the patients consider their symptoms to be absent or mild and that their medication is effective. The treatment will be individualized by the treating physician according to signs

and symptoms of the disease and patient characteristics. If TNFi therapy fails, switching to another TNFi alternative or an anti-IL-17 therapy may be considered.

All included patients will be on stable medical treatment with TNFi for the last 6 months. Patients will be instructed to use NSAIDs should they experience minor worsening of symptoms, but if the patients experience significant symptom worsening and suspect a severe disease worsening (flare) or adverse events, they will be instructed contact the hospital (Table 1). A visit will be arranged within two weeks to allow for examination and documentation of disease status. Concomitant medication will be recorded in the CRF, with particular attention to registration of use of NSAIDs, oral or injected glucocorticoid, and analgesics for residual pain (paracetamol or opioids).

Patients in all three study arms will be instructed to take blood tests for assessment of safety and side effects each 3rd month as prescribed and monitored by their general practitioner. Patients, who normally take these 3-month blood tests at the hospital due to convenience, may continue this practice.

5.1.2 Usual care arm

Patients in the “Usual care” arm will be treated according to current conventional follow-up regimen with regular hospital visits. In the ReMonit study this includes prescheduled face-to-face visits with an experienced rheumatology nurse at 6 and 12 months and with a rheumatologist at 18 months (study end), with a review of disease-related concerns, blood test results, joint examination as well as recording medication use, and adverse events.

5.1.3 Remote monitoring arm

The patients in this study arm will download the app, MyDignio, on their smartphone or tablet and receive a brief introduction on the use of MyDignio from the study coordinator. MyDignio app will be used for reporting PROs, displaying results (histograms) for PROs over time, and for asynchronous (chat) communication with HPs. The patients will receive a SMS reminder for “tasks” (e.g., self-reporting PROs or uploading a photo with blood test results each 6th month) according to the planned time points as outlined in 7.2- 7.3. The patients will receive an automatic reminder when a task is uncompleted.

A subgroup of patients (n= 10-15) will use a CPR instrument for home-based monthly self-measurements of CRP. The patients will register the CRP value in the MyDignio app.

The patients will be asked to wear a wrist band/smart watch for physical activity monitoring over 12 months. They will be instructed to wear this activity tracker at least 10 hours during daytime, but they can wear the water-resistant tracker all day and night should they want to. The number of steps and mean pulse levels will be collected per minute for research purposes.

A study coordinator/nurse will once daily (Monday to Friday) log on to the digital platform, Dignio Prevent, to monitor the PROs and respond to potential patient messages/questions. By setting acceptable maximum and minimum values for the outcomes (see table 2), a triaging functionality in the Dignio Prevent software will aid the study coordinator/nurse in highlighting PROs or measurements that needs attention. The software will also indicate if the patient misses one or more self-reports or measurement registrations.

The patients can send a message to the HP through the app, and HPs can reply or call the patient to investigate if there is a need to schedule a visit. The software uses a standardized application program interface, and all communication through the software is encrypted and in compliance with current legislation.

5.1.4 Patient-initiated care arm

Patients in this arm will also download the app, MyDignio, on their smartphone or tablet and receive a brief introduction from the study coordinator. The app will be used to collect PROs. Patients are instructed to contact the hospital if they need an evaluation regarding medication, symptoms worsening or adverse events. The patients will receive a SMS reminder for “tasks” (e.g. self-reporting or uploading a photo with blood test results each 6 months) according to the planned time points as outlined in 7.2-7.3. The patients will receive an automatic reminder if the task is not completed.

Table 1: Indication for unscheduled/extra visits for all three study arms

Indication	Definition	Action
Significant worsening	Patient-reported significant symptoms worsening	The HP excludes other potential reasons for the experienced worsening. If there is a need for changing medication, a physical examination or blood test, a visit will be scheduled within two weeks
Significant adverse effects	Safety laboratory test results showing adverse effects or patient-reported adverse events	Schedule a visit within two weeks

Table 2: Indication for the HPs to contact a patient in the Remote monitoring study arm

Indication	Definition	Action
Significant worsening	Yellow flag: BASDAI ≥ 4 in the monthly PRO reporting Red flag: BASDAI ≥ 8 in the monthly PRO reporting	The study nurse contacts the patient to evaluate if a hospital visit is needed
The patient has requested to be contacted by HP	The patient sends a message in MyDignio app asking to be contacted by HP	The study nurse contacts the patient to evaluate if a hospital visit is needed

¹ PGA: Patient Global Assessment of disease activity

5.2 Measures to Minimize Bias: Randomization and Blinding

Eligible patients will be allocated in a 1:1:1 ratio between the three study arms. A statistician and a secretary, not involved in patient screening or enrollment, will provide a computer-generated block randomization list, and prepare sealed, opaque envelopes containing information on study arm assignment. Details of block size and allocation sequence generation will be provided in a separate document unavailable to those who enroll patients or assign treatment. The study does not include blinding of participant and treating health care personnel.

5.3 Study Intervention Compliance

Compliance to treatment will be assessed as the proportion of completed self-reports at all time points for self-reporting and the proportion who register their blood test results at 6- and 12-months. Full

compliance is defined as completion of $\geq 80\%$ of all frequent self-reports and 100% of all half-year self-reports and blood test results. Partial compliance is less than full, but $\geq 60\%$ completed frequent self-reports, and 2 half-year self-report and blood test result registered. Low compliance is $< 60\%$ completed frequent self-reports, and only 1 half-year self-report and 1 blood test result registered.

Full compliance to medical treatment is defined as taking the treatment as prescribed, partial compliance is less than 100% but more than 70% compliant to prescribed treatment, and low compliance is less than 70% compliant. Reason for non-compliance (lack of efficacy/adverse events/concurrent medical condition/patient wish/other) will be assessed.

6 Discontinuation of Study Intervention and Participant Discontinuation/Withdrawal

6.1 Discontinuation of Study Intervention

Patients who for some reason withdraw from following the treatment protocol will be asked to continue follow-up in the study.

6.2 Participant Discontinuation/Withdrawal from the Study

Patients have the right to withdraw from the study at any time for any reason. In the case that a patient decides to prematurely withdraw from the study, he or she should be asked if they can still be contacted for further information, so that a final evaluation can be made with an explanation of why the patient is withdrawing from the study, including assessment of possible adverse events. Although a subject is not obliged to give his or her reason(s) for withdrawing prematurely from a trial, the investigator should make a reasonable effort to ascertain the reason(s), while fully respecting the subject's rights. If possible, at the last visit of the patient all assessments of the "Early discontinuation of study visit" will be done.

6.3 Lost to Follow up

A participant will be considered lost to follow-up if he or she repeatedly fails to return for scheduled visits or to complete self-reports and is unable to be contacted by the study site. If a participant in the "Usual care" arm fails to return to the clinic for a required study visit, the study coordinator must attempt to contact the participant and reschedule the missed visit as soon as possible and counsel the participant on the importance of maintaining the assigned visit schedule and ascertain whether the participant wishes to and/or should continue in the study. If a participant in any of the two, new follow-up strategy arms fail to report the half-year self-reports and register blood test results, the study coordinator must attempt to contact the participant and counsel the participant on the importance of maintaining the self-report schedule and ascertain whether the participant wishes to and/or should continue in the study. Before a participant is deemed lost to follow up, the coordinator must make every effort to regain contact with the participant (where possible, 3 telephone calls and, if necessary, a certified letter to the participant's last known mailing address or local equivalent methods). These

contact attempts should be documented in the participant's medical record. Should the participant continue to be unreachable, he/she will be considered to have withdrawn from the study.

7 Study Assessments and Procedures

Study procedures and their timing are summarized in the Schedule of Activities. Adherence to the study design requirements, including those specified in the Schedule of Activities, is essential and required for study conduct.

7.1 Study visits

7.1.1 Screening

All screening evaluations as outlined in the Schedule of Activities must be completed and reviewed to confirm that potential participants meet all eligibility criteria. The investigator will maintain a screening log to record details of all participants screened and to confirm eligibility or record reasons for screening failure, as applicable.

Procedures conducted as part of the participant's routine clinical management and obtained before signing of the informed consent form may be used for screening purposes provided the procedures met the protocol-specified criteria and were performed within the time frame defined in the Schedule of Activities. Laboratory measures preformed < 14 days prior to screening can be used.

7.1.2 Assignment of intervention and subject numbering

Eligible patients will be assigned a unique patient identification number. Once assigned, this number cannot be reused for another patient. The patients will be randomized 1:1:1 to the three arms as described in section 5.1.

7.1.3 Baseline visit

At the baseline visit all assessments outlined in 7.2. and 7.3 except AE/SAE will be assessed. In addition, the following data will be recorded:

- Demography: age, sex, education, work status
- General medical history: previous and current comorbidities and previous and current medications
- Disease specific medical history: symptom duration, date of diagnosis, current and previous SpA-features (peripheral arthritis, enthesitis), SpA associated disease (uveitis, psoriasis, inflammatory bowel disease), family history of SpA and SpA associated diseases.
- Fulfilment of ASAS criteria including HLA B27, X-ray and/or MRI findings on sacroiliac (SI) joints and spine as documented in the patient journal
- Lifestyle factors: tobacco use and physical activity last seven days (frequency, intensity, and duration)
- Patient satisfaction with care
- Self-efficacy/confidence related to using smartphone, tablet, computer, app's, secure login and digital health services: 6 items with response categories: Never used, Very bad, Bad, Neither good nor bad, Good, Very good
- eHealth literacy (20 items from 4 domains from the eHealth Literacy Questionnaire (eHLQ)³³: 1) using technology to process health information, 2) ability to actively engage with digital services, 3) feel safe and in control, 4) motivated to engage with digital services. Response options range from 1 (strongly disagree) to 4 (strongly agree).

7.1.4 Regular visits

Assessments are as outlined in the Schedule of Activities and in section 7.2.

7.1.5 Unscheduled visits

HPs can freely schedule additional visits as required according to clinical judgement. If patients in any of the three study arms suspects a disease worsening or AE, he or she should contact the hospital and be seen there within two weeks as the latest. Unscheduled visit will, if possible, include all assessments of a regular visit.

7.1.6 End of study visit

The end of the study visit will be performed at 18 months and will include a formal end of study assignment in the eCRF. The patients will self-report their satisfaction with care.

7.1.7 Withdrawal visit

A withdrawal visit (early discontinuation) will include all assessments of a regular visit in addition to an assessment of reason for withdrawal and time of withdrawal.

7.2 Efficacy assessments

7.2.1 Patient-reported outcome measures

At Baseline (after screening, but before the randomization), patient demographics and PROs be collected using a digital device at the hospital.

Every 6. month, patients will receive a link a digital survey ("Nettskjema" (Services for sensitive data (TSD), University of Oslo)). Collection of a few PROs from patients will be done monthly for the Remote monitoring arm and every third month for the Patient-initiated care arm using the MyDignio app. The participants in these two intervention arm will also report blood test results every 6. month using the MyDignio app.

- **Patient global assessment of disease activity** (PGA) (Visual Analogue Scale, NRS 0-10) (All arms: Baseline, 6-, 12- and 18-months) (Remote monitoring arm: each month) (Patient-initiated care arm: each 3rd month)
- **Patient-reported flares** (All arms: 6-, 12- and 18-months) (Remote monitoring arm: each month) (Patient-initiated care arm: each 3rd month)
If the patient responds "yes" or "uncertain" to the question if they have experienced a significant worsening of symptoms (reflecting a flare in disease activity), they will be asked which date the flare occurred and the number of days it lasted.
- **Bath Ankylosing Spondylitis Disease Activity Index** (BASDAI) (All arms: Baseline, 6-, 12- and 18-months) (Remote monitoring arm: each month if disease worsening) (Patient-initiated care arm: each 3rd month if disease worsening)
BASDAI is a 6 item questionnaire (NRS 0-10) used to assess disease activity in ankylosing spondylitis³⁴. The score is the sum (of the first four individual questions and the mean of questions five and six) divided by five.
- **Bath Ankylosing Spondylitis Functional Index** (BASFI) (Baseline)
BASFI is a 10 item questionnaire (NRS 0-10) used to assess disease activity in ankylosing spondylitis³⁴. The score is the sum of each individual question divided by 10.
- **Patient-reported pain (general)** Single item (NRS 0-10) (Baseline, 6-, 12- and 18-months)

- **Patient-reported joint pain** Single item (NRS 0-10) (Baseline, 6-, 12- and 18-months)
- **Patient-reported global change in disease activity.** Single item with seven-point response scale ranging from "Much worse" to "Much better" (6-, 12- and 18-months)
- **Patient-reported global change in activity impairment.** Single item with seven-point response scale ranging from "Much worse" to "Much better" (6-, 12- and 18-months)
- **Euro Quality of Life 5 Dimensions 5 Levels (EQ5D-5L)** (Baseline, 6-, 12- and 18-months)
EQ-5D is a utility instrument for measurement of health related quality of life³⁵ and is applicable to a wide range of health conditions and treatments, it provides a simple descriptive profile and a single index value for health status.
- **Work Productivity and Activity Impairment (WPAI)** – item no. 6 on activity Impairment (NRS 0-10) (Baseline, 6-, 12- and 18-months).
- **Questions on physical activity from the HUNT study** (Baseline, 6-, 12- and 18-months) The HUNT questionnaire consists of 3 questions assessing frequency, intensity, and duration of physical activity in the past 7 days³⁶.
- **Sleep disturbance** (Baseline, 6-, 12- and 18-months) 1 item from the Pittsburgh Sleep Quality Index measuring sleep disturbance due to pain with four-point response categories ranging from "Not during the past month" to "Three or more times a week"³⁷.
- **Patient satisfaction with care** (Baseline, 6-, 12- and 18-months)
Satisfaction with the care provided (from patient experience questionnaires) includes one item with five point response options ranging from "Very satisfied" to "Very dissatisfied"³⁸.
- **Medication use** (Baseline, 6-, 12- and 18-months)
Questions on whether the patient has taken the TNFi medication as instructed, and if NSAIDs, glucocorticoid (oral or injections) or analgesics have been used.
- **Time and costs related to consultations** (Baseline)
The time being absent from work and potential travel costs related to consultations will be registered.

7.2.2 Clinical examination/assessment

Clinical assessments will be performed as outlined for each element below. If possible, assessments of individual patients will be performed by the same assessor. Training in clinical examination will be provided for all assessors

- **General clinical examination** (baseline visit)
- **Heel enthesitis and peripheral arthritis assessment** (all visits)

Assessment of heel enthesitis is done by palpating with sufficient pressure to blanch the anterior part of the examiner's fingernail and scored as yes/no. For assessment of peripheral arthritis, the following joints are examined for tenderness and swelling: proximal interphalangial joints (1-5), metacarpophalangial joints (1-5), wrists, elbows, shoulders, knees, ankles, metatarsophalangial joints. Both tenderness and swelling are scored as yes/no.

7.2.3 Laboratory assessment

Assessment of inflammatory markers will be performed prior to each hospital visit by the hospital laboratory and includes ESR (mm/hr) and CRP (mg/L). All patients will be instructed to take standard care blood samples (hemoglobin, red blood cells, white blood cells with differential count, platelets, creatinine, and alanine transaminase) as a safety procedure when using TNFi as prescribed and monitored by their general practitioner. Patients, who normally take these blood tests at the hospital due to convenience, may continue this practice. Patients in the “Remote monitoring” and the “Patient-initiated care” arms are instructed to report blood test results each 6th month in the MyDignio app. These blood tests will in addition be used to assess clinical safety (see 7.3.3). A small subgroup in the Remote monitoring group will receive a CRP-instrument and be asked to measure their CRP monthly and register the value in the MyDignio app.

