1.2 Schema

1.3 Schedule of Activities

Procedure	Screening		Intervention Period [remote monitoring/visits]					Extra visits and early discontinuation
			Baseline	Every month	6 th month follow-up	12 th month follow-up	18 th month Study end	
Inclusion and exclusion criteria	X							
Fulfilment ASAS criteria ¹	X							
Physical examination incl. heart and lungs	X							
Informed consent	X							
Safety laboratory tests ²		X		X	X	X	X	
CRP and ESR		X	(X ³)	X	X	X	X	
Clinical examination of disease activity, incl. enthesitis (heel), peripheral arthritis		X		X ⁴	X ⁴	X	X	
Vital signs ⁵		X						
Medical history		X						
Demography		X						
Lifestyle		X						
Patient global assessment		X	X ⁶	X	X	X	X	
Patient-reported outcomes		X	X ⁶	X	X	X	X	
Medication review		X		X	X	X	X	
Randomization		X						
Adverse event review				X	X	X	X	
Reason for discontinuation ⁷							X	

¹ The ASAS criteria include: Sacroilitis on imaging, HLA-B27 and SpA features (see 9.5.1)

² Patients using biologic medication, including the tumour necrosis factor inhibitors (TNFis), are instructed to take safety laboratory tests each 3rd month. For the “Usual care” arm, the patients will take blood tests at the 6th month visit at the hospital and take an additional blood test between these visits, which normally is prescribed and monitored by their general practitioner. For the “Remote monitoring” and “Patient-initiated care” arms, the patients are instructed to take blood tests each 3rd month, which normally is prescribed and monitored by their general practitioner. Patients, who normally take the 3-month blood tests at the hospital due to convenience, may continue this practice.

Each 6th month the patients in the two latter arms will be requested to upload a photo of the blood test results into the MyDignio app.

³ Only for the subgroup n=15 in the “Remote monitoring” arm that receive a home-based CRP instrument

⁴ At 6 and 12 months only in the “Usual care” arm

⁵ Pulse, blood pressure, body weight and height

⁶ Patients in the “Remote monitoring” arm will complete a brief questionnaire each month, and patients in the “Patient-initiated care” only each 3rd month. Longer questionnaires will be completed by all study arms each 6th month.

⁷ Only at “Early discontinuation” visit

Abbreviations: CRP: C-Reactive Protein, ESR: Erythrocyte Sedimentation Rate, HLA-B27: Human Leucocyte Antigen B27

2 Introduction

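### CRP and ESR are scheduled at 6 and 12 months in every arm, but for most patients in the two new arms the protocol names no sample that supplies either marker

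*Protocol*

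**What the plan says.** **What is required.** The primary endpoint is the proportion with ASDAS below 2.1 at 6, 12 and 18 months (Protocol 3.2.2, 8.4.2). Section 7.2.4 gives a CRP formula and an ESR formula, and neither works without its marker. In the Schedule of Activities (1.3) the CRP/ESR row is marked at 6, 12 and 18 months. The only footnote on that row, number 3, concerns the monthly column: "Only for the subgroup n=15 in the" remote monitoring arm. The clinical-examination row, by contrast, carries footnote 4: "At 6 and 12 months only in the" usual care arm.

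**What is supplied.** Section 7.2.3 gives the source of both markers: "Assessment of inflammatory markers will be performed prior to each hospital visit by the hospital laboratory and includes ESR (mm/hr) and CRP (mg/L". Section 5.1.2 gives usual care "prescheduled face-to-face visits with an experienced rheumatology nurse at 6 and 12 months"; the new arms have no such visits at those times. Section 7.2.3 itemises the samples prescribed and monitored by the general practitioner as "standard care blood samples (hemoglobin, red blood cells, white blood cells with differential count, platelets, creatinine, and alanine transaminase". Under Schedule footnote 2, which is attached to the safety-laboratory row, patients in the new arms "will be requested to upload a photo of the blood test results into the MyDignio app" every sixth month. Section 7.2.3 adds of the reported results: "These blood tests will in addition be used to assess clinical safety". Home CRP is limited to the remote arm: "A subgroup of patients (n= 10-15" (5.1.3).

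**The concern.** The Schedule and the endpoint ask for a marker at 6 and 12 months in all arms, while the sample list for the new arms does not contain one. A patient and a general practitioner who follow the list in 7.2.3 to the letter would produce an upload that looks complete but from which ASDAS cannot be calculated. A marker that was never measured in that sample cannot be supplied later by the analysis.

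Any such loss would be confined to the two experimental arms of a non-inferiority comparison, at two of its three time points. Usual care would be unaffected because its hospital visits bring hospital sampling. The compliance definition (5.3), the loss-to-follow-up procedure (6.3) and the automatic reminders (5.1.3, 5.1.4) speak only of blood test results or of a task left undone. None of them requires the result to contain CRP or ESR.

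**Working it through.** The protocol gives no figure of its own on this point to reproduce. The check sets the possible sources side by side and then counts.

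**Step 1: sources of CRP or ESR at months 6 and 12 in the two new arms**

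| Possible source | Where | Marker named? |
|---|---|---|
| Hospital sample before a visit | 7.2.3 | Yes, but no prescheduled visit at these times |
| General-practitioner sample, uploaded as a photo | 7.2.3, Schedule footnote 2, Appendix 2 | No |
| Same 3-monthly tests taken at the hospital for convenience | 7.2.3, Appendix 2 | No; the text refers to the same tests |
| Home CRP instrument | 5.1.3, Schedule footnote 3 | CRP only, 10-15 remote-arm patients |
| Unscheduled or early-discontinuation visit | Schedule, 7.1.5, 7.1.7 | Yes, but not a planned 6- or 12-month sample |

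The lists in 7.3.3 and Appendix 2 Table 6 also omit CRP and ESR, but they carry little weight. They are safety lists that cover hospital visits too, and at hospital visits 7.2.3 does provide both markers. The evidence is the itemised list in 7.2.3.

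Month 18 is not affected: there is an end-of-study visit (7.1.6), and hospital visits include the markers.

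**Step 2: patients with no named source**

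Inputs: 80 per arm (8.2), so 2 × 80 = 160 in the new arms; home-CRP subgroup 10-15.

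- Subgroup of 15: 160 − 15 = 145, and 145/160 = 90.6%.
- Subgroup of 10: 160 − 10 = 150, and 150/160 = 93.8%.

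**Step 3: worst case for ASDAS values**

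Planned post-baseline values: 240 patients × 3 times = 720.

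- 145 × 2 = 290, and 290/720 = 40.3%.
- 150 × 2 = 300, and 300/720 = 41.7%.

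This assumes that no upload and no unscheduled or early-discontinuation visit ever supplies a marker.

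**Step 4: weight of the marker in the score**

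CRP term: 0.58 × ln(CRP + 1). The CRP values are illustrative assumptions.

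- CRP 1 mg/L: 0.58 × ln 2 = 0.40, which is 19% of 2.1.
- CRP 5 mg/L: 0.58 × ln 6 = 1.04, which is 49% of 2.1.
- CRP 10 mg/L: 0.58 × ln 11 = 1.39, which is 66% of 2.1.

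The four patient-reported items alone therefore do not settle which side of the cut-off a patient is on.

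**The case against.** The strongest reply is that the marker was plainly intended.

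- The risk table in 2.3.1 relies on the six-monthly patient-registered results to reveal loss of efficacy, which a haematology, creatinine and ALT panel would not do.
- The objectives table in 2.3.4 lists the six-monthly blood tests, next to monthly CRP, as a source on fluctuations in disease activity.
- In 7.2.3 the safety use is described as additional, so the first use must be something else.
- Section 8.4.1 describes the full analysis set by a completed questionnaire and blood test result, while 8.3 describes it by an assessment of the primary endpoint. Read together, the blood result is the laboratory part of ASDAS.

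All of this stands. It rules out one tempting reading, that the protocol never planned to measure CRP in the new arms. It does not remove the gap, because none of these passages tells the person ordering the sample to include the marker, and the one itemised list leaves it out.

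A second reply also stands in part. In the remote arm, laboratory results are reviewed every six months (Appendix 2), staff log on each weekday and the software flags missed registrations (5.1.3). A missing CRP could well be seen there. A reader might infer that a result without a marker passes unnoticed in both arms, but the documents do not support that for remote monitoring. It fits patient-initiated care better, where Appendix 2 reserves the results for research once the 18-month follow-up is over. Even in the remote arm, no rule makes the marker a condition of a registered result.

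Finally, patient instructions outside this document may name the marker, and the visible text cannot exclude that.

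**Conclusion.** The point holds as an internal conflict that bears on the primary endpoint. The Schedule requires CRP and ESR at 6 and 12 months without arm restriction. Section 7.2.3 provides them only before hospital visits, and its itemised general-practitioner sample names neither. On the planned numbers, 145-150 of 160 new-arm patients (91-94%) have no named source at those two times, leaving aside unscheduled and early-discontinuation visits. That the Schedule marks apply to all arms is read from the absence of a footnote and from the endpoint times; no sentence states it.

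The figure of 290-300 of 720 values (40-42%) is a ceiling. A reader might take it as the expected loss, but the evidence of intent points the other way: the actual loss is unknown and probably well below it. What can be said firmly is that any loss from this gap would fall only on the experimental arms, and that the risk of its going unnoticed is greatest in patient-initiated care. The wording should be corrected, but the point does not show that the design fails.

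**What to change.** 1. Reconcile 7.2.3, Appendix 2 and Schedule footnote 2 with the CRP/ESR row. State that the 6- and 12-month samples of both new arms include CRP, with ESR as the fallback allowed in 7.2.4 or as the Schedule requires.
2. In 5.3 and 6.3, count the half-year blood result as registered only if it shows CRP or ESR.
3. Amend the sentence in Appendix 2 on patient-initiated results so that it permits an administrative check, at receipt, that a marker is present, without clinical review of the values. As written, that sentence would not allow the check.

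The cost is a few sentences, and an analyte the Schedule already requires on blood already being drawn. The downside is slightly more follow-up of incomplete uploads. Because the uploaded photo shows all the values, staff must also keep the presence check separate from monitoring, so that the patient-initiated arm remains unmonitored.
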